receiving placebo reported dry eye (n=1). All eye disorders AEs were of mild to moderate intensity, resolved spontaneously (without treatment), and were more frequently reported with highest dose (40 mg). Among them, the AEs of blurred vision, photophobia (“Increased ocular light sensitivity”), visual impairment (“distorted contrast perception”, “distorted colour perception”) reported by 8 out of 47 subjects receiving emodepside were considered as treatment-related by the Investigator. Also of note, at the highest dose (40 mg), lightheadedness (n=1), dizziness (n=1) or headache (n=1) were reported concomitantly to blurred vision.

None of the volunteers met any of the protocol-specified withdrawal criteria and overall tolerability to emodepside has been acceptable up to 20 mg. The presence of post-dose visual disturbances in subjects of Cohort 8 receiving either 40 mg solution or placebo may warrant some concern and escalation was stopped at this dose level.

The pharmacokinetic results obtained so far show that T_{max} for the LSF solution is consistently about 1 h post-dose when fasted. Mean C_{max} and AUC for the LSF solution have been roughly dose-proportional, with low to moderate inter-individual variability. The plasma half-life during the first 24 h is very short for a single dose of emodepside. After 3, 7, 16 and 47 h the maximum plasma concentration is reduced to 50%, 25%, 12.5% and 6.25% respectively. Terminal plasma half-life is 523 h. Although data of Cohort 9 (which was treated with a single dose of emodepside with food) are still under review, administration of the LSF of 10 mg with a high fat, high-calorie meal resulted in a clinically relevant food effect with a reduction of AUC to ~67%, C_{max} to 42% and a delay of the T_{max} up to 2.33 h. Therefore, the recommendation of administration of the emodepside (LSF) under fasted conditions is given.

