- on Day 0: before and at 1, 2, 3, 4, 6, 8 and 12 h after the morning dose
 - on Days 1–8: before the morning dose
 - on Day 9: before and at the following times after the morning dose: 0.5, 1, 2, 3, 4, 6, 8, 12, 24, 36 (Day 10), 48 (Day 11), 72 (Day 12), 96 (Day 13) and 120 h (Day 14)
 - at outpatients visits on Days 17, 20, 23 and 27 (± 2 days), and long-term follow-up visits (Days 60, 90 and 120 ± 2 days)
12. Blood samples for assay of emodepside in plasma will be taken:
- on Day 0: before and at 0.25, 0.5, 1, 1.5, 2, 2.5, 3, 4, 6, 8, 12, and 15 h after the morning dose
 - on Days 1–8: before the morning dose
 - on Day 9: before and at the following times after the morning dose: 0.25, 0.5, 1, 1.5, 2, 2.5, 3, 4, 6, 8, 12, 15, 24, 36 (Day 10), 48 (Day 11), 72 (Day 12), 96 (Day 13) and 120 h (Day 14)
 - at outpatients visits on Days 17, 20, 23 and 27 (± 2 days), and at Follow-up (Day 30 ± 2 days)
- Subjects should rest in the supine position for 10 minutes before blood is drawn (if possible).
13. Blood samples for assay of metabolites of emodepside in plasma will be taken:
- on Day 0: before and at 0.25, 0.5, 1, 1.5, 2, 2.5, 3, 4, 6, 8, 12, and 15 h after the morning dose
 - on Day 9: before and at 0.25, 0.5, 1, 1.5, 2, 2.5, 3, 4, 6, 8, 12, and 15 h after the morning dose
14. Urine for assay of emodepside and its metabolites may be collected at the following time points:
- On Day 0: from 0–4, 4–8, 8–12 and 12–24 h after the morning dose
 - On Day 9: from 0–4, 4–8, 8–12 and 12–24 h after the morning dose
15. Blood and urine samples for clinical laboratory safety tests (haematology, biochemistry, coagulation & urinalysis) will be taken: at Screening Visit 1; on Day –1 (–24 h before the morning dose on Day 0); before the morning dose on Day 0; before the morning dose on Days 1, 5 and 8; before, 24 h (Day 10) and 120 h after the morning dose on Day 9 (Day 14); at the Day 23 outpatient visit (± 2 days); at Follow-up (Day 30 ± 2 days); and at long-term follow-up (Days 60, 90 and 120 ± 2 days).
- Subjects should rest in the supine position for 10 minutes before blood is drawn (if possible).
16. Serology tests will comprise HIV 1 & 2, hepatitis B & C, and HbA1c
17. Blood samples for measurement of leptin and prolactin will be taken at Screening Visit 1 and before the morning dose on Day 9.
18. Subjects will be admitted to the ward on Day 119, before the Day 120 long-term follow-up visit.

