MRT _{last}	Mean Residence Time from time zero (pre-dose) to the time of last quantifiable concentration will be calculated using

$$MRT_t = \frac{AUMC_t}{AUC_t}$$

Where AUMC_t is the area under the first moment of the concentration-time curve from time zero (pre-dose) to the time of last quantifiable concentration

V_z/F Apparent volume of distribution will be calculated using the following formula:

$$V_z / F = \frac{Dose}{\lambda_z \bullet AUC_\infty}$$

Multiple Dose Day 9 parameters

λ_z	The terminal rate constant will be estimated by log-linear regression analysis on data points visually assessed to be on the terminal log-linear phase.
$t_{1/2}$	The terminal half-life will be calculated according to the following equation: $t_{1/2} = \ln 2 / \lambda_z$.
$t_{1/2,dom}$	The dominant half-life will be calculated from the terminal slope of the log concentration-time (0-24h) curve according to the following equation: $t_{1/2,dom} = \log_e 2 / \lambda_z$
AUC_{last}	The area under the concentration-time curve from time zero (pre-dose) to the time of last quantifiable concentration will be calculated using a trapezoidal method.
AUC_{last}/D	The area under the concentration-time curve from time zero (pre-dose) to the time of last quantifiable concentration, corrected for dose.
$AUC_{last,norm}$	The area under the concentration-time curve from time zero (pre-dose) to the time of last quantifiable concentration corrected by dose and body weight
AUC_{12}	Area under the plasma concentration-time curve during a 12 h dosing interval
AUC_{12}/D	Area under the plasma concentration-time curve during a 12 h dosing interval corrected for dose
$AUC_{12,norm}$	Area under the plasma concentration-time curve during a 12 h dosing interval corrected by dose and body weight
AUC_{24}	Area under the plasma concentration-time curve during a 24 h dosing interval
AUC_{24}/D	Area under the plasma concentration-time curve during a 24 h dosing interval corrected for dose
$AUC_{24,norm}$	Area under the plasma concentration-time curve during a 24 h dosing interval corrected by dose and body weight
AUC_{∞}	The area under the plasma drug concentration vs. time curve from time zero to infinity.
AUC_{∞}/D	The area under the plasma drug concentration vs. time curve from time zero to infinity, corrected for dose.
$AUC_{\infty,norm}$	The area under the concentration-time curve from time zero to infinity corrected by dose and body weight

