AUC ₂₄ /Dose **	Dose-normalised AUC from time zero to 24 h	The dose-normalised AUC from time zero to 24h will be calculated as AUC ₂₄ /Dose Administered	(h*ng/mL)/mg	Y	-	AUCINTD	AUC ₂₄ /D
AUC _{24, norm} **	Area under the concentration-time curve from time zero to 24h corrected by dose and body weight	The AUC from time zero to 24h normalised by dose and body weight will be calculated as AUC ₂₄ /(Dose administered*body weight)	(h*ng/mL)/(mg*kg)	Y	-	AUCINTWD	AUC _{24, norm}
Clearance, volume of distribution and mean residence time							
V _z /F	Apparent volume of distribution during terminal phase after non-intravenous administration	Apparent volume of distribution will be calculated using the following formula: $V_z / F = \frac{Dose}{\lambda_z \cdot AUC_{\infty}}$	L	Y	V _z _pred (actually derives V _z _F_pred for oral dose)	VZFP	V _z /F
MRT _{last}	Mean Residence Time	The mean residence time will be calculated using: $MRT = \frac{AUMC}{AUC_{\infty}}$	h	Y	MRTLST_pred	MRTEVLST	MRT _{last}

* Calculated only for Cohort 3

**Calculated only for Cohorts 1 and 2

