MRT _∞	Mean Residence Time extrapolated to infinity	The mean residence time will be calculated using: $MRT = \frac{AUMC}{AUC_{\infty}}$	h	Y	MRTINF_pred	MRTEVIFP	MRT _∞
Accumulation and time invariance ratios							
R _{ac} (AUC _t)	Accumulation ratio for AUC	Accumulation ratio will be calculated from AUC _t at steady state and AUC _t after single dose	-	N	-	ARAUC	R _{ac} (AUC _t)
R _{ac} (C _{max})	Accumulation ratio for C _{max}	Accumulation ratio will be calculated from C _{max} at steady state and C _{max} after single dose	-	N	-	ARCMAX	R _{ac} (C _{max})

* Calculated only for Cohort 3

**Calculated only for Cohorts 1 and 2

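### The SAP formula for Day 0 MRT_last (AUMC/AUC_inf, with AUMC undefined) conflicts with the protocol's AUMC_t/AUC_t and with the row's own to-last labels

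*SAP*

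**What the plan says.** Protocol 8.4.2, among the Day 0 parameters, describes MRT_last as "Mean Residence Time from time zero (pre-dose) to the time of last quantifiable concentration" and gives the formula AUMC_t/AUC_t. It then defines the numerator: "Where AUMC_t is the area under the first moment of the concentration-time curve", stopped at the last quantifiable concentration.

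SAP Appendix B 3.1.1 lists the same Day 0 parameter. The row says "The mean residence time will be calculated using" and prints AUMC/AUC_inf. AUMC has no subscript and is not defined. The other cells of the row name a to-last quantity: text symbol MRT_last, CDISC term MRTEVLST, table symbol MRT_last. The WinNonlin field is MRTLST_pred.

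SAP Appendix B 3.1.2 prints the same AUMC/AUC_inf expression for the Day 9 parameter defined as "Mean Residence Time extrapolated to infinity".

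The SAP Introduction undertakes to identify substantial differences in statistical methods from the protocol. Nothing is noted at this row.

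**The concern.** A residence time to the last quantifiable concentration needs both areas stopped at that time. An extrapolated denominator makes the result depend on a terminal slope that MRT_last is meant to avoid. It also leaves the SAP with one formula for two different parameters. A programmer working from the printed formula would not produce the protocol's quantity and could not tell from the SAP which numerator to use. What is at stake is the correctness of one exploratory Day 0 summary and the SAP's agreement with the protocol.

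**Working it through.** Neither document states an MRT value, so there is no plan figure to reproduce. The check is algebra followed by an illustration.

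**Algebra.** Let f be the extrapolated share of AUC_inf, so AUC_t = (1 − f) × AUC_inf.

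- If AUMC is truncated, AUMC_t/AUC_inf = (1 − f) × AUMC_t/AUC_t. This is always below MRT_last.
- If AUMC is extrapolated, AUMC_inf/AUC_inf = (1 − f) × AUMC_t/AUC_t + f × (t_last + 1/λz). This is always above MRT_last, because the tail's mean time exceeds t_last.

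**Inputs.**

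- Decline, Protocol 1.4: "After 3, 7, 16 and 47 h the maximum plasma concentration is reduced to 50%, 25%, 12.5% and 6.25% respectively". Tmax is about 1 h (same section). Cmax is set to 100.
- Day 0 sampling, Protocol 5.1: early times, then "2.5, 3, 4, 6, 8, 12, and 15 h after the morning dose". The Day 1 pre-dose sample supplies about 24 h.
- AUC method, SAP Appendix B 1.2: linear when rising, logarithmic when falling.
- Extrapolation half-life (assumed): 11 h (dominant, Protocol 1.5); 31 h (concentration halves between 16 and 47 h, and 47 − 16 = 31); 523 h (terminal, Protocol 1.4); or a fit by the adjusted-R² rule of SAP Appendix B 1.3, which selects the last four points. The fit uses the predicted last concentration (Appendix B 1.4).
- The protocol does not say whether the decline times run from dose or from Tmax, so both are shown.

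**One row in full** (times from dose, 11 h). C at 24 h = 12.5 × 0.5^(8/31) = 10.45, and λz = ln 2/11 = 0.0630. The trapezoids give AUC_t = 596.3 and AUMC_t = 4656.3.

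- AUC_inf = 596.3 + 10.45/0.0630 = 762.2
- AUMC_inf = 4656.3 + 24 × 165.9 + 165.9/0.0630 ≈ 11,270
- Protocol: 4656.3/596.3 = 7.81 h
- SAP, truncated: 4656.3/762.2 = 6.11 h
- SAP, extrapolated: 11,270/762.2 = 14.79 h

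**All rows, t_last 24 h.** The percentage shortfall under the truncated reading equals the extrapolated share.

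| Times from | Half-life | AUC_inf | Extrapolated share | AUMC_t/AUC_t (h) | AUMC_t/AUC_inf (h) | AUMC_inf/AUC_inf (h) |
|---|---|---|---|---|---|---|
| Dose | 11 h | 762.2 | 21.8% | 7.81 | 6.11 | 14.79 |
| Dose | 14.5 h (fitted) | 802.3 | 25.7% | 7.81 | 5.80 | 17.33 |
| Dose | 31 h | 1063.8 | 43.9% | 7.81 | 4.38 | 34.58 |
| Dose | 523 h | 8483.1 | 93.0% | 7.81 | 0.55 | 724.35 |
| Tmax | 11 h | 828.4 | 20.5% | 7.68 | 6.11 | 14.27 |
| Tmax | 13.5 h (fitted) | 856.0 | 23.0% | 7.68 | 5.91 | 15.91 |
| Tmax | 31 h | 1136.8 | 42.1% | 7.68 | 4.45 | 33.35 |
| Tmax | 523 h | 8723.9 | 92.4% | 7.68 | 0.58 | 720.32 |

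With t_last 15 h and an 11 h half-life, the protocol formula gives about 5.3 h, the truncated reading about 3.7 h (30 to 31% low) and the extrapolated reading about 13 h (2.4 to 2.5 times).

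**Cohort 3.** The evening dose falls about 12 h after the morning dose (Protocol 7.1 and 8.3.6), but Day 0 sampling runs to 15 h. A last-quantifiable cut-off would therefore take in evening-dose drug. Neither document states a cut-off for MRT_last, although the companion AUC for this cohort stops at 12 h.

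**The case against.** The strongest reply is that this is a slip in one formula cell with no effect on output. Parameters are calculated in WinNonlin, and the row's symbol, CDISC term and field name all say to-last, so the reported value may match the protocol anyway. That possibility stands, but the documents do not establish it. They never define what MRTLST_pred computes. SAP Appendix B 1.4 reserves predicted versions for parameters that depend on λz, which a true MRT_last does not, and the AUC_last row carries no such suffix. The field name points both ways.

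A reader might infer that the SAP formula understates MRT_last. That needs a truncated numerator, which the SAP does not state. Because the expression is identical to the MRT_inf row, an extrapolated numerator is an equally natural reading, and it overstates.

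A reader might also infer that AUC_inf cannot be estimated on Day 0. That is too strong: Vz/F in the adjacent Day 0 row, and in the protocol, already uses it. The weaker statement is fair. In the 15 h and 24 h scenarios examined, more than 20% of AUC_inf is extrapolated. SAP Appendix B 1.2 restricts use above 20% and calls use above 40% unacceptable without justification. The SAP does not say whether those limits extend to derived parameters. Losses above 90% arise only with the 523 h half-life, which a Day 0 fit would not produce.

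One caution also stands. Subscripts in this SAP table should be confirmed against the signed document, because the %AUCextrap row in 3.1.2 shows x in the text copy where the protocol shows infinity.

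**Conclusion.** Wrong as written, and minor. The conflict with the protocol, the duplicated MRT_inf formula and the absence of any note of departure are plain from the text and need no assumption. The numerical effect is conditional. At 24 h, with an 11 h or Day 0-fitted half-life, the value is about 20 to 26% low under a truncated numerator and 1.9 to 2.2 times the protocol value under an extrapolated one. These figures are illustrative: they rest on preliminary single-dose decline data and an assumed extrapolation slope. A wrong reported value is possible but not shown. MRT_last is exploratory and only summarised, and the pharmacokinetic escalation limit is on Cmax, so no dose decision depends on it.

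**What to change.** In SAP Appendix B 3.1.1, print MRT_last = AUMC_last/AUC_last. Define AUMC_last as the first-moment area from zero to the last quantifiable concentration, and make the WinNonlin entry name a field confirmed to compute that ratio. Leave AUMC/AUC_inf for MRT_inf in 3.1.2, with AUMC there marked as extrapolated to infinity.

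For Cohort 3, add that the Day 0 profile used for MRT_last ends at 12 h, before the evening dose, in line with AUC_12. This fills a gap left by both documents and is separate from the formula error.

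The cost is one corrected row, a subscript in a second and one sentence in the SAP. No new data are needed, and the protocol formula stays as it is.

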3.1.2 Multiple Dose

Emodepside parameters to be calculated on Day 9.

Text Symbol	Definition	Calculation	Typical Units	Log Transform	WNL	CDISC Controlled Terminology	TFL Symbol
Concentrations during and after multiple dosing							
C_{trough}	Trough plasma concentration	Trough plasma concentration (measured concentration at the end of a dosing interval at steady state [taken directly before next administration]) obtained directly from the concentration-time data.	ng/mL	Y	-	CTROUGH	C_{trough}
Concentrations and times (after final dose)							
$C_{\text{max,ss}}$	Maximum (peak) plasma concentration at steady state	The maximum (peak) plasma concentration will be obtained directly from the concentration-time data.	ng/mL	Y	Cmax	CMAX	$C_{\text{max,ss}}$
$C_{\text{max,ss}}/\text{Dose}$	Dose-normalised C_{max} at steady state	The dose-normalised C_{max} will be calculated as $C_{\text{max}}/\text{Dose}$ administered	(ng/mL)/mg	Y	Cmax_D	CMAXD	$C_{\text{max,ss}}/D$
$C_{\text{max,ss,norm}}$	Observed maximum plasma concentration corrected by dose and body weight at steady state	The C_{max} normalised by dose and body weight will be calculated as $C_{\text{max}}/(\text{Dose administered} * \text{body weight})$	(ng/mL)/(mg*kg)	Y	-	CMAXWD	$C_{\text{max,ss,norm}}$
t_{max}	Time to reach maximum (peak) plasma concentration	The first time of maximum (peak) plasma concentration will be obtained directly from the concentration-time data.	h	N	Tmax	TMAX	t_{max}
Half-life (after final dose)							
λ_z	Terminal rate constant	The apparent terminal phase rate-constant (λ_z) will be estimated by linear regression of logarithmically transformed concentration versus time data.	1/h	Y	Lambda_z	LAMZ	λ_z
$t_{1/2}$	Terminal half-life	The terminal half-life calculated from the terminal slope of the log concentration-time curve, as follows: $t_{1/2} = \frac{\log_e 2}{\lambda_z}$	h	Y	HL_Lambda_z	LAMZHL	$t_{1/2}$
$t_{1/2,\text{dom}}$	Dominant half-life	The dominant half-life calculated from the terminal slope of the log concentration-time (0-24h) curve, as follows:	h	Y	HL_Lambda_z	LAMZHLD	$t_{1/2,0-24}$

Text Symbol	Definition	Calculation	Typical Units	Log Transform	WNL	CDISC Controlled Terminology	TFL Symbol
		$t_{1/2, dom} = \frac{\log_e 2}{\lambda_z}$					
Areas under the curve (after final dose)							
AUC _{last}	Area under the plasma concentration-time curve from time zero to time of last measurable concentration	The area under the concentration-time curve from zero time (pre-dose) to the time of last quantifiable concentration will be calculated using the (specified) trapezoidal method.	h*ng/mL	Y	AUClast	AUCLST	AUC _{last}
AUC _{last} /Dose	Dose-normalised AUC from time zero to last measurable concentration	The dose-normalised AUC from time zero to last measurable concentration will be calculated as AUC _{last} /Dose Administered	(h*ng/mL)/mg	Y	-	AUCLSTD	AUC _{last} /D
AUC _{last,norm}	Area under the concentration-time curve from time zero to time of last measurable concentration corrected by dose and body weight	The AUC from time zero to last measurable concentration normalised by dose and body weight will be calculated as AUC _{last} /(Dose administered*body weight)	(h*ng/mL)/(mg*kg)	Y	-	AUCLSTWD	AUC _{last,norm}
AUC ₁₂ *	Area under the plasma concentration-time curve from time zero to time 12 h	The area under the concentration-time curve from zero time (pre-dose) to time 12 h will be calculated using the (specified) trapezoidal method. If λ_z is not estimable, a partial AUC is not calculated (when $t_{last} < t$).	h*ng/mL	Y	User specified area	AUCINT	AUC ₁₂
AUC ₁₂ /Dose *	Dose-normalised AUC from time zero to 12 h	The dose-normalised AUC from time zero to 12h will be calculated as AUC ₁₂ /Dose Administered	(h*ng/mL)/mg	Y	-	AUCINTD	AUC ₁₂ /D
AUC _{12,norm} *	Area under the concentration-time curve from time zero to 12h corrected by dose and body weight	The AUC from time zero to 12h normalised by dose and body weight will be calculated as AUC ₁₂ /(Dose administered*body weight)	(h*ng/mL)/(mg*kg)	Y	-	AUCINTWD	AUC _{12,norm}

Text Symbol	Definition	Calculation	Typical Units	Log Transform	WNL	CDISC Controlled Terminology	TFL Symbol
AUC ₂₄ **	Area under the plasma concentration-time curve from time zero to time 24 h	The area under the concentration-time curve from zero time (pre-dose) to time 24 h will be calculated using the (specified) trapezoidal method. If λ_2 is not estimable, a partial AUC is not calculated (when $t_{last} < t$).	h*ng/mL	Y	User specified area	AUCINT	AUC ₂₄
AUC ₂₄ /Dose **	Dose-normalised AUC from time zero to 24 h	The dose-normalised AUC from time zero to 24h will be calculated as AUC ₂₄ /Dose Administered	(h*ng/mL)/mg	Y	-	AUCINTD	AUC ₂₄ /D
AUC _{24, norm} **	Area under the concentration-time curve from time zero to 24h corrected by dose and body weight	The AUC from time zero to 24h normalised by dose and body weight will be calculated as AUC ₂₄ /(Dose administered*body weight)	(h*ng/mL)/(mg*kg)	Y	-	AUCINTWD	AUC _{24, norm}

Text Symbol	Definition	Calculation	Typical Units	Log Transform	WNL	CDISC Controlled Terminology	TFL Symbol
AUC _∞	Area under the plasma concentration-time curve from time zero to infinity	The area under the concentration-time curve will be calculated using the (specified) trapezoidal method for the interval 0 to t _{last} (time t _{last} is the time at which the last non-zero level was recorded), plus the area under the exponential curve from t _{last} to infinity, calculated as follows: $AUC_{t-\infty} = \frac{\hat{C}_t}{\lambda_z}$ where \hat{C}_t is the predicted value of the concentration at t _{last} .	h*ng/mL	Y	AUCINF_pred	AUCIFP	AUC _{inf}
AUC _∞ /Dose	Dose-normalised AUC from time zero to infinity	The dose-normalised AUC from time zero to infinity will be calculated as AUC _∞ /Dose Administered	(h*ng/mL)/mg	Y	-	AUCIFPD	AUC _∞ /D
AUC _{∞,norm}	Area under the concentration-time curve from time zero to infinity corrected by dose and body weight	The AUC from time zero to infinity normalised by dose and body weight will be calculated as AUC _∞ /(Dose administered*body weight)	(h*ng/mL)/(mg*kg)	Y	-	AUCIFPWD	AUC _{∞,norm}
%AUC _{extrap}	Percentage of AUC _∞ extrapolated from from t _{last} to infinity	$\% AUC_{extrap} = \frac{100 \times AUC_{t-x}}{AUC_x}$	%	N	AUC_%EXTRAP_pred	AUCPEP	%AUC _{extrap}
Clearance, volume of distribution and mean residence time (after final dose)							
CL _{SS} /F	Apparent total clearance from plasma after oral administration	Apparent total clearance from plasma will be calculated using the following formula: $CL_{SS} / F = \frac{Dose}{AUC_t}$	L/h	Y	Clss_pred (actually derives Clss_F_pred for oral dose)	CLFTAU	CL _{SS} /F
V _z /F	Apparent volume of distribution after non-intravenous administration calculated at steady state	Apparent volume of distribution calculated at steady state will be calculated using the following formula: $V_z / F = \frac{Dose}{\lambda_z \cdot AUC_t}$	L	Y	Vz_pred (actually derives Vz_F_pred for oral dose)	VZFTAU	V _z /F

Text Symbol	Definition	Calculation	Typical Units	Log Transform	WNL	CDISC Controlled Terminology	TFL Symbol
MRT _∞	Mean Residence Time extrapolated to infinity	The mean residence time will be calculated using: $MRT = \frac{AUMC}{AUC_{\infty}}$	h	Y	MRTINF_pred	MRTEVIFP	MRT _∞
Accumulation and time invariance ratios							
R _{ac} (AUC _t)	Accumulation ratio for AUC	Accumulation ratio will be calculated from AUC _t at steady state and AUC _t after single dose	-	N	-	ARAUC	R _{ac} (AUC _t)
R _{ac} (C _{max})	Accumulation ratio for C _{max}	Accumulation ratio will be calculated from C _{max} at steady state and C _{max} after single dose	-	N	-	ARCMAX	R _{ac} (C _{max})

* Calculated only for Cohort 3

**Calculated only for Cohorts 1 and 2

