1.5. Assessment and management of risk

The factors taken into account in the assessment of risk to subjects in this study are as follows:

- The planned daily doses of emodepside have been administered to humans as single doses and were well tolerated. Based on the first-in-human clinical study, overall tolerability to emodepside has been acceptable up to 20 mg. Post-dose visual disturbances were observed more frequently at 40 mg, and although these visual and nervous system disturbances were considered non-serious and mild in intensity, dose escalation was stopped at this dose level. All visual disturbances were transient in nature and resolved spontaneously within 24 h, and without treatment.
- During the study, the dose will be increased only if the PK, safety and tolerability of the previous dose is acceptable and if the investigator and sponsor's medical representative agree that it is appropriate to give a higher dose. The next planned dose level may be reduced, or a dose level may re-tested or an intermediate dose level selected, based on emerging data. The total daily dose will not exceed 20 mg emodepside (as LSF solution at a concentration of 1 mg/mL).
- Subjects will undergo a comprehensive ophthalmology assessment at screening and will be excluded from the study if any ocular pathology is detected. Additional ophthalmology assessments will be performed during the study, if clinically indicated.
- Subjects will undergo a full neurological assessment at screening, Day 0 and at discharge from the ward in order to detect and assess any neurological disorder or change.
- In the first-in-human trial (DNDI-EMO-01), emodepside was shown to undergo bi-phasic elimination with a dominant half-life ($t_{1/2\ 0-24}$) estimated at approximately 11 h, and terminal half-life ($t_{1/2\ 0-\infty}$) over 520 h. In order to comprehensively assess safety parameters over this period, volunteers will be followed up until Day 120.

2. Study Objectives and Endpoints

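### The dominant half-life is derived only from the Day 9 0-24 h curve, where carry-over from 9 or 18 earlier doses flattens the slope, so it is not comparable with the single-dose value of about 11 h or between OD and BID

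*SAP*

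**What the plan says.** SAP Appendix B 3.1.2 (Multiple Dose) opens with "Emodepside parameters to be calculated on Day 9". Under the half-lives after the final dose it lists t1/2,dom: "The dominant half-life calculated from the terminal slope of the log concentration-time (0-24h) curve, as follows". The output symbol is t1/2,0-24. Protocol 8.4.2 has the parameter among the Multiple Dose Day 9 parameters: "The dominant half-life will be calculated from the terminal slope of the log concentration-time (0-24h) curve according to the following equation". It is absent from the Day 0 lists in both documents (protocol 8.4.2, SAP Appendix B 3.1.1).

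Protocol 1.5 uses the same 0-24 h label for the first-in-human single-dose value, "estimated at approximately 11 h". Protocol 1.4 describes the single-dose curve: "After 3, 7, 16 and 47 h the maximum plasma concentration is reduced to 50%, 25%, 12.5% and 6.25% respectively", and "Terminal plasma half-life is 523 h".

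No correction for carry-over is described, and no regression window is fixed for this parameter. SAP Appendix B 1.3 selects the points with the largest adjusted R², with at least three points. Protocol 8.4.2 speaks of points assessed visually.

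**The concern.** One label covers two quantities. In the first-in-human study it is the decline over 24 h after a single dose. In this study it is the decline of the last dose plus whatever remains from all earlier doses.

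The log slope of a sum is the concentration-weighted mean of the log slopes of its parts. Each earlier dose is on a later, flatter part of its own curve, so the sum falls more slowly than a single dose would. More earlier doses mean more flattening, so BID reads longer than OD.

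With unchanged kinetics, the tables would show a t1/2,0-24 well above 11 h, and longer for BID than OD. A reader who set those figures beside the single-dose report could take them for slower elimination on repeated dosing, or for an effect of the BID regimen. PK after multiple doses is a secondary objective, so the output should not invite that reading.

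**Working it through.** **Inputs.** Protocol 1.4: peak at about 1 h fasted; 50%, 25%, 12.5% and 6.25% of Cmax at 3, 7, 16 and 47 h; terminal half-life 523 h; Cmax and AUC roughly dose-proportional, which supports superposition. Schedule of events: plasma samples at 6, 8, 12, 15 and 24 h on Day 9, and to 15 h on Day 0 with the Day 1 pre-dose sample as the 24 h point. Doses before the Day 9 morning dose: 9 (OD) or 18 (BID).

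**Assumptions.** Linear kinetics; mean curve without noise; log-linear interpolation between the stated points. The protocol does not say at what level the 523 h phase begins, so I start it at 6.25% of Cmax (straight after the last stated point), 3% or 1%. Until then the last stated slope continues (12.5% to 6.25% over 47 − 16 = 31 h, a 31 h half-life). The stated hours are read as time after dose, and alternatively as time after the peak (1 h later). Cohort 3 is taken to have no evening dose on Day 9.

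**Formulas.**
- OD: C9(t) = C(t) + Σ C(t + 24k), k = 1 to 9
- BID: C9(t) = C(t) + Σ C(t + 12k), k = 1 to 18
- Half-life = ln 2 / (−slope of ln C on t)

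**Reproducing the single-dose figure.** Regression over 6-24 h on the single-dose curve gives 12.3 h (hours after dose) or 11.1 h (hours after peak), in line with about 11 h. Other windows do not: 3-24 h gives 8.4 to 9.4 h, 8-24 h gives 13.5 to 14.5 h, and 12-24 h gives 16 to 18 h.

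**Worked case.** Hours after dose, 523 h phase from 6.25%. Concentrations relative to single-dose Cmax:

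| Time | Single dose | Day 9 OD | Day 9 BID |
|---|---|---|---|
| 6 h | 0.297 | 0.833 | 1.411 |
| 24 h | 0.1045 | 0.601 | 1.122 |

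For example, C(6) = 0.5 × 0.5^(3/4) = 0.297 and C(24) = 0.125 × 0.5^(8/31) = 0.1045. A two-point check, 18 × ln 2 / ln(C6/C24), gives 11.9 h, 38 h and 54 h; the five-point regressions below agree. Earlier doses supply 1 − 0.1045/0.601 = 83% (OD) and 1 − 0.1045/1.122 = 91% (BID) of the 24 h concentration.

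**6-24 h window, all cases** (half-life in h, ratio to Day 0 in brackets):

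| Hours read as | 523 h phase from | Day 0 | Day 9 OD | Day 9 BID |
|---|---|---|---|---|
| after dose | 6.25% | 12.3 | 40.0 (3.3) | 56.8 (4.6) |
| after dose | 3% | 12.3 | 26.5 (2.2) | 34.1 (2.8) |
| after dose | 1% | 12.3 | 19.7 (1.6) | 24.1 (2.0) |
| after peak | 6.25% | 11.1 | 34.6 (3.1) | 49.8 (4.5) |
| after peak | 3% | 11.1 | 23.5 (2.1) | 30.8 (2.8) |
| after peak | 1% | 11.1 | 17.8 (1.6) | 22.3 (2.0) |

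**Other windows.** Over 3-24, 8-24 and 12-24 h with the same starting levels, the same-window ratio of Day 9 to Day 0 runs from 1.48 to 3.46 (OD) and from 1.66 to 4.71 (BID).

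**Bounding case.** With no 523 h phase at all, which contradicts protocol 1.4, the 6-24 h values are still 16 to 18 h (OD) and 20 to 21 h (BID). The slope flattened in every run.

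**SAP point-selection rule.** On these curves the adjusted-R² rule picks 8, 12, 15 and 24 h on Day 0 (13.5 to 14.5 h) but 12, 15 and 24 h on Day 9 (25 to 63 h OD, 29 to 85 h BID). Left free, it would not even use the same window on the two days.

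**The case against.** The strongest reply is that nothing here is mislabelled within its own table. The row sits among half-lives after the final dose in a Day 9 table, and the decline after the last of repeated doses is a legitimate thing to describe. Carry-over is visible elsewhere: Ctrough on Days 1 to 9, the accumulation ratios and the terminal half-life are all reported. The parameter is in no endpoint list (protocol 2.2.3 and 2.3, SAP 4.2.2), and no comparison with 11 h is planned. All of this stands and keeps the priority modest. It does not remove the problem that the output symbol is the one protocol 1.5 attaches to the single-dose value.

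Three stronger readings are tempting but not supported:

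- *That the Day 9 value is 1.5 to 4.7 times 11 h.* Those are ratios to the same-window Day 0 slope. Divided by 11 h, the same runs give about 1.2 to 7.7, because that mixes carry-over with the choice of window, and none of the three windows behind that range (3-24, 8-24 and 12-24 h) returns 11 h on Day 0.
- *That this half-life sets the dosing interval for later studies.* Neither document says so.
- *That it would create a false dose effect between 5 mg and 10 mg.* Cohorts 1 and 2 both receive ten once-daily doses, so under linear kinetics both are inflated equally. Only OD against BID is distorted.

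**Conclusion.** The concern holds as a point about comparability. As defined, t1/2,dom includes carry-over and cannot be compared with the single-dose value of about 11 h, or between OD and BID, even if kinetics are unchanged. It is not wrong as a description of the Day 9 decline.

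The direction follows from linear kinetics and a curve that flattens with time, and it appeared in every case tested. The size is model-dependent. It rests on linear superposition of a mean curve, on where the 523 h phase is assumed to start and on the regression window, so the ranges should be read as orders of magnitude. There is no allowance for assay noise or for differences between subjects.

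**What to change.** 1. Add t1/2,dom to the Day 0 parameters for Cohorts 1 and 2 (SAP Appendix B 3.1.1, protocol 8.4.2), using the existing samples with the Day 1 pre-dose sample as the 24 h point.
2. Pre-specify one regression window for it, for example 6-24 h, in place of the adjusted-R² selection. Use only this value for comparison with the single-dose study.
3. Relabel the Day 9 value as the apparent 0-24 h decline after the last dose, including carry-over, with its own symbol. State that it is not to be compared with 11 h, with Day 0, or between OD and BID. Alternatively, drop it.
4. For Cohort 3, do not compare a Day 0 slope with 11 h. The second dose cuts that curve at 12 h, and a 4-12 h slope on the single-dose curve gives only about 5.6 to 6.3 h.
5. Reconcile the statements on the Cohort 3 evening dose on Day 9. Protocol 4.3 and 7.1 give evening doses on Days 0 to 9. The protocol summary, the schedule footnote on administration and section 8.3.8 give a morning dose only on Day 9. A dose at 12 h would break any 0-24 h slope in that cohort.

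The cost is one more PK output and small wording changes in both documents. No new samples are needed.
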